##### Interim analyses

Not applicable.

##### Methods for additional analyses (e.g. subgroup analyses)

Not applicable.

Methods in analysis to handle protocol non-adherence and any statistical methods to handle missing data

We perform statistical analysis on complete case. The researcher will contact participants as much as possible to supplement missing data. The missing data will be assessed using an intention-to-treat analysis.

Plans to give access to the full protocol, participant level-data and statistical code

The data sharing will be available upon request and with permission and

approval from the Pinggu Hospital of Beijing Traditional Chinese medicine hospital.

[figure not shown]

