## **Type of Units Assigned**

### **Period(s)**

The duration of the trial is 38 weeks for each patient, including a 2-week baseline assessment (week 0-2), 12-week treatment period (week 1-12), and 24-week follow-up (week 13-36).

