### **3. Outcome Measures**

#### **Primary outcome**

The primary outcome in this trial is the change in the average of VAS-BP scores in the first 2 weeks of menstruation, recorded in the patient daily diary.

The VAS-BP will be measured using a 10cm linear VAS with 0 representing no pain and 10 the worst imaginable pain from baseline at weeks 4, 8, and 12.

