### **Statistical analysis**

Sample size estimation was based on changes in the breast pain VAS(VAS-BP) score. According to the pre-trial, the VAS-BP score significantly decreased by  $2.98 \pm 0.95$  in MA group compared to  $2.35 \pm 0.97$  in the SM group after treatment from baseline. In the current trial, we assume a significance level  $\alpha = 0.05$  and power  $(1-\beta) = 0.90$ , and providing for a two-sided outcome, at least 42 participants will be required for each group, as calculated by PASS version 11.0 (NCSS, LLC, Kaysville, UT, USA), assuming a two-tailed test with a 20% drop-out rate, a total of 108 patients (54 in each group) will be recruited.

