#### 4. Adverse event reporting and harms

All adverse events will be documented in the CRF throughout the trial. Adverse events related to acupuncture (such as severe pain, local hematoma, infection and abscess, and broken needles ), including discomfort after treatment, will be recorded in time and detail. A detailed description of the categories, severity and correlation with the treatment of the adverse events will be collected by patients themselves and evaluators. If the adverse event is severe and associated with the trial, the patient will be withdrawn from the study and given appropriate medical care.

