## Statistical Analysis Plan

Statistical methods for primary and secondary outcomes

We will use SPSS 22.0 software (IBM SPSS Statistics; IBM Corp, Somers, NY) to perform all statistical analyses following the intention-to-treat principle. The CI will be established at 95%, and the significance level at 0.05. For continuous data, the data will be presented as mean  $\pm$  standard deviation when normally distributed or presented as median (IQR) when not normally distributed. Statistical comparisons will be performed by the independent-sample t tests or Wilcoxon rank-sum test for continuous data and by X-test or Fisher exact test for categorical data, as appropriate. A p-value  $<0.05$  will be considered statistically significant.

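### The plan calls its analyses intention-to-treat but specifies complete cases, and it names no method for outcomes that stay missing

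*Combined protocol and SAP*

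**What the plan says.** The SAP, and the identical paragraph in the protocol under Statistical methods for primary and secondary outcomes, commits the team "to perform all statistical analyses following the intention-to-treat principle". The tests named there are the t test, Wilcoxon rank-sum, chi-square and Fisher exact tests. The SAP contains no missing-data rule.

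The only missing-data text is in the protocol, in the paragraph on non-adherence and missing data that follows Methods for additional analyses. It has three sentences:

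- Sentence 1 sets who is analysed: "We perform statistical analysis on complete case".
- Sentence 2 plans an effort to recover absent values by getting back in touch with patients.
- Sentence 3 returns to the general principle: "The missing data will be assessed using an intention-to-treat analysis".

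The sample-size section allows for attrition: "assuming a two-tailed test with a 20% drop-out rate, a total of 108 patients (54 in each group) will be recruited". It does not say what period the 20% covers. Under Period(s), "The duration of the trial is 38 weeks for each patient". The primary outcome is the change in VAS-BP, and the section gives three assessment times without choosing one ("the worst imaginable pain from baseline at weeks 4, 8, and 12"). Table 1 schedules VAS-BP at weeks 0, 4, 8 and 12, among other times.

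**The concern.** For a patient with no outcome value, the two instructions pull apart. A complete-case rule drops the patient. Intention-to-treat says who belongs in the analysis and in which arm, but it does not supply the absent value. The third sentence of the missing-data paragraph therefore does not resolve the first. The named tests do not help either, because each uses observed values only.

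Two analysts could follow this plan faithfully, analyse different sets of patients for the primary outcome, and both call the result intention-to-treat. The choice could also be made after the data are seen. If drop-out is related to outcome differently in the two arms, the complete-case difference is biased. The MA effect is overstated if only MA drop-outs did worse than completers, and understated if only SA drop-outs did.

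**Working it through.** **1. The rules side by side**

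| Place | What it fixes | Patient whose outcome stays missing |
|---|---|---|
| Protocol, Statistical methods; SAP | Intention-to-treat for all analyses | Belongs in the analysis; no method given |
| Missing-data paragraph, sentence 1 | Complete cases | Left out |
| Sentence 2 | Contact participants | Reduces missingness; silent on what remains |
| Sentence 3 | Intention-to-treat | Names a principle, no method |

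The readable text contains no imputation, mixed model, sensitivity analysis or definition of the analysis set.

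**2. The plan's attrition figure**

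The plan needs 42 per arm: 42 / 0.80 = 52.5, rounded up to 53, against 54 stated. The drop-out step is reproduced to within one patient. The 42 itself is a separate matter: the stated inputs at two-sided 5% and 90% power give 49 by the normal formula. It does not enter this point, which uses only 108 and 20%.

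**3. How many could be left out**

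- All 20% lost by the analysis time point: 0.20 x 108 = 21.6, about 22, leaving about 86 (54 x 0.80 = 43.2 per arm).
- 20% accruing at a constant rate over the 36 weeks after allocation (assumption): 1 - 0.80^(12/36) = 7.2% by week 12; 0.072 x 108 = 7.7, about 8 (4 per arm).

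**4. Illustration of effect on the result**

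Assumptions, none from the documents except the means and SDs: week 12 is the endpoint; completers show the planned changes, 2.98 (SD 0.95) for MA and 2.35 (SD 0.97) for SA, a difference of 0.63; losses are equal by arm. The deficits below are invented for illustration.

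Complete case, SE = sqrt((0.95² + 0.97²)/n):

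- n = 43 per arm: SE 0.207, t = 0.63/0.207 = 3.04, p = 0.003.
- n = 50 per arm: SE 0.192, t = 0.63/0.192 = 3.28, p = 0.001.

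A deficit of d cm among one arm's drop-outs moves the difference by d x (drop-outs/54). For d = 1.0 this is 11/54 = 0.204 with 11 lost, or 4/54 = 0.074 with 4 lost. Equal deficits at equal rates cancel. The p-values come from normal multiple imputation within arm (20,000 imputations, small-sample degrees of freedom):

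| Deficit in drop-outs | 43 observed + 11 lost per arm | 50 observed + 4 lost per arm |
|---|---|---|
| MA only, 1.0 cm | 0.43 (95% CI -0.004 to 0.86), p = 0.052 | 0.56, p = 0.006 |
| SA only, 1.0 cm | 0.83, p = 0.0002 | 0.70, p = 0.0005 |
| Both, 1.0 cm | 0.63, p = 0.006 | 0.63, p = 0.002 |
| MA 1.0, SA 0.5 cm | 0.53, p = 0.018 | not run |
| MA only, 0.63 cm | 0.50, p about 0.02 | not run |
| None | 0.63, p = 0.003 | not needed |

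In the last row, imputation with no deficit gives essentially the complete-case answer. Every shift in the table comes from the assumed deficits.

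**The case against.** Intention-to-treat is often used loosely. The plan can be read as analysing patients as randomised, on available data, after trying to recover the rest. The third sentence may also be poor wording for an imputation the authors had in mind. That is a fair reading of intent, but the plan does not define its analysis set that way, and on either reading no method is named for values that stay missing.

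A second objection is that the numbers do not show harm. This largely stands. A reader might infer from the table that complete-case analysis would produce a false positive. The documents do not support that: they give no drop-out reasons or rates by arm, and only one scenario crosses 0.05. That scenario needs all 20% lost by week 12 and a 1.0 cm deficit in MA drop-outs only, which is larger than the whole planned effect of 0.63.

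A reader might also infer that replacing complete case with imputation or a mixed model would remove the bias. It would not do so by itself. Both assume missing at random, and the shifts shown arise when that assumption fails. Gains from using the week 4 and 8 values are plausible but are not quantified here.

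Finally, a reader might take the adverse-event section ("If the adverse event is severe and associated with the trial, the patient will be withdrawn from the study") as a further contradiction of intention-to-treat. It is not one. It leaves open only whether outcome data are still collected from those patients.

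**Conclusion.** The inconsistency is real and needs to be fixed before analysis. A stated complete-case rule conflicts with a stated intention-to-treat principle, and no method covers outcomes that stay missing. This rests on the text alone and holds at any drop-out rate; it does not depend on the illustrative p-values.

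The scale is about 22 of 108 patients at the planned 20%. Actual loss could be higher. It could be lower if data recovery works, or about 8 by week 12 if the 20% accrues evenly over the 36 weeks after allocation. The direction and size of any bias are unknown.

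**What to change.** **Required.** Put one consistent rule in the protocol's statistical methods section, its missing-data paragraph and the SAP:

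- Analyse all randomised patients by assigned arm.
- Name a primary method that uses the VAS-BP values already scheduled at weeks 0, 4, 8 and 12. This can be multiple imputation, which keeps patients with no post-baseline value. It can also be a baseline-adjusted repeated-measures mixed model, with an explicit statement of how such patients are treated, since they add nothing to that model.
- Keep complete case as a supportive analysis, labelled as such.
- Add a simple delta-adjusted sensitivity analysis in which the deficit can differ by arm, because the primary method assumes missing at random and would not by itself correct outcome-related drop-out.

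**Recommended only.** State the period that the 20% covers. Clarify whether outcome data are still collected from patients withdrawn after an adverse event.

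**Cost.** Wording changes and modest analysis work, with no new visits or measurements. The downside is that the primary result then relies on the missing-at-random assumption. The team should check that its software can run the delta-adjusted analysis.

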#### 4. Adverse event reporting and harms

All adverse events will be documented in the CRF throughout the trial. Adverse events related to acupuncture (such as severe pain, local hematoma, infection and abscess, and broken needles ), including discomfort after treatment, will be recorded in time and detail. A detailed description of the categories, severity and correlation with the treatment of the adverse events will be collected by patients themselves and evaluators. If the adverse event is severe and associated with the trial, the patient will be withdrawn from the study and given appropriate medical care.

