##### Arm/Group Description

##### MA group

Acupuncture rationale was based on the theory of TCM, which is closely related to the liver. When reviewing the literature on breast pain, people believe that "Stagnation of liver qi and stagnation of Qi and blood" is a good explanation for the important mechanism of breast pain attack. We will select Ashi points (the most obvious local pain over the breast), Tanzhong(CV17), bilateral Wuyi (ST15), Rugen (ST18), Tianzong(SI11), Geshu (BL17), Ganshu(BL18), Hegu(LI4), Sanyinjiao (SP6) and Taichong (LR3)in this trial. The location of the above acupoints will be based on the nomenclature and location of acupuncture points drafted by the National Standard of the People' s Republic of China (GB/T 12 346-2006) [1]. Sterile single-use stainless steel needles (size 0.3 mm × 40 mm) (Hwato brand, Suzhou Medical Appliance Factory, China) will be utilized. After local skin disinfection with 75% alcohol wipes while patients are in a sitting position, then fix the adhesive pad (to ensure the implementation of a blind method, the acupuncture group is placed with the same

fixed adhesive pad as the sham acupuncture group). Acupuncturists will insert needles horizontally into the Wuyi(ST15), Rugen (ST18), and Ashi points toward the mammary duct to a depth of 15 – 20 mm; horizontally into tanzhong(CV17) downward to a depth of 5 – 10 mm, perpendicularly into Hegu(LI4), Sanyinjiao (SP6), Tianzong(SI11), and Taichong (LR3) to a depth of approximately 15 – 25 mm. Obliquely into Geshu (BL17) and Ganshu(BL18) to a depth of approximately 15-20mm. The depth of needling will vary based on the participant's body size. After insertion, all needles will be manually manipulated (equal manipulations of twirling, lifting, and thrusting) to achieve De qi sensation, which is defined as a composite of unique needling sensations, including soreness, numbness, distention, or heaviness felt by both participants and acupuncturists [2]. All the needles will be retained for 30 min and then gently removed.

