#### Statistical methods

##### Statistical methods for primary and secondary outcomes

We will use SPSS 22.0 software (IBM SPSS Statistics; IBM Corp, Somers, NY) to perform all statistical analyses following the intention-to-treat principle. The CI will be established at 95%, and the significance level at 0.05. For continuous data, the data will be presented as mean  $\pm$  standard deviation when normally distributed or presented as median (IQR) when not normally distributed. Statistical comparisons will be performed by the independent-sample t tests or Wilcoxon rank-sum test for continuous data and by X-test or Fisher exact test for categorical data, as appropriate. A p-value  $< 0.05$  will be considered statistically significant.

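### Read as written, a severe trial-related adverse event removes a woman from the study, not only from acupuncture, so her later outcome and safety assessments are lost

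*Combined protocol and SAP*

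**What the plan says.** The last sentence of protocol section 4 sets a trigger, "If the adverse event is severe and associated with the trial", and a consequence: "the patient will be withdrawn from the study and given appropriate medical care". The same section also says "All adverse events will be documented in the CRF throughout the trial".

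On analysis, the protocol's statistical methods and the separate Statistical Analysis Plan both undertake "to perform all statistical analyses following the intention-to-treat principle". The protocol's missing-data paragraph, under Methods for additional analyses, says "We perform statistical analysis on complete case. The researcher will contact participants as much as possible to supplement missing data". It then adds "The missing data will be assessed using an intention-to-treat analysis", without naming a method.

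Table 1 schedules VAS-BP, NDBP and safety at weeks 4, 8, 12, 24 and 36. WHOQOL-BREF, the two ultrasound measures and the global improvement rating are due at week 12.

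**The concern.** Stopping treatment and leaving the study are different events. A woman harmed by the needling may need to stop acupuncture, but she can usually still fill in a pain diary and report on her health. The rule makes no such distinction. It is also not ordinary dropout: the protocol removes her, whether or not she wishes to leave.

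Two things are at stake. First, intention to treat means comparing women as randomised. A rule that creates missing outcomes after randomisation, for a reason tied to treatment, works against that when the analysis uses complete cases. The women removed may also differ in outcome: severe pain heads the protocol's list of acupuncture-related events, and the primary outcome is breast pain. Second, scheduled safety follow-up would end for the women in whom it matters most. Medical care continues, but care is not scheduled data collection.

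Loss could also differ by arm. In the MA arm, "Acupuncturists will insert needles horizontally", among other insertions, while the sham needle only touches the skin. This is an inference: no event rates by arm are given, and severe pain or discomfort can occur in either arm.

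**Working it through.** **The text.** The rule has no figure of its own to reproduce, so the first check is a reading of the provisions together.

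- Section 4 removes the woman from the study. No sentence continues her diary, questionnaires, ultrasound or safety visits.
- The missing-data paragraph analyses complete cases and gives no method that would keep a woman without data in the comparison.
- If the event falls before week 12, she loses the remaining primary-outcome time points, the week-12 secondary outcomes, and weeks 24 and 36.
- If it falls after week 12, only weeks 24 and 36 are affected when complete case is applied per visit. If it is applied per patient, she could drop out of the week 4 to 12 comparisons as well. The plan does not say which.

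**Inputs for scale**, from the protocol's Statistical analysis section: improvement 2.98 (SD 0.95) in MA and 2.35 (SD 0.97) in sham (SA); target difference 2.98 − 2.35 = 0.63 cm; 54 per arm; and a plan made "with a 20% drop-out rate", so 54 × 0.8 = 43.2, about 43 per arm. (By the usual formula these inputs need 49 to 50 per group for two-sided 90% power, not the stated 42. That is a separate matter and does not enter here.)

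**Assumptions.** One woman is lost before week 12. The others in her arm improve by the arm mean. Other dropout is either nil (n = 54) or unrelated to outcome (n = 43). Her true improvement is m.

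**Formula.** With her, the MA mean would be ((n − 1) × 2.98 + m)/n; without her it is 2.98. Leaving her out therefore shifts MA − SA by (2.98 − m)/n. For a sham woman the shift is −(2.35 − m)/n.

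| Woman lost | m | Shift, n = 54 | Shift, n = 43 |
|---|---|---|---|
| MA, typical | 2.98 | 0 | 0 |
| MA, one SD worse | 2.03 | +0.95/54 = +0.018 | +0.95/43 = +0.022 |
| MA, one SD better | 3.93 | −0.018 | −0.022 |
| MA, no improvement | 0 | +2.98/54 = +0.055 (8.8% of 0.63) | +2.98/43 = +0.069 (11.0%) |
| SA, typical | 2.35 | 0 | 0 |
| SA, one SD worse | 1.38 | −0.97/54 = −0.018 | −0.97/43 = −0.023 |
| SA, one SD better | 3.32 | +0.018 | +0.023 |
| SA, no improvement | 0 | −2.35/54 = −0.044 | −2.35/43 = −0.055 |

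Shifts are in cm. For k women in one arm with the same m, multiply by k. The no-improvement MA case lies 2.98/0.95 = 3.1 SD below the arm mean, so it is extreme.

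**Against sampling error.** SE = √((0.95² + 0.97²)/n), which is 0.185 at 54 per arm and 0.207 at 43. The one-SD MA shift is 0.0176/0.1848 = 9.5% and 0.0221/0.2071 = 10.7% of it.

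**Power.** By a two-sided t test, power is 0.922 with 54 and 54, and 0.920 with 53 and 54. Loss of power is not the issue.

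**The case against.** Non-collection is inferred: the protocol does not say that assessments stop. The promise to contact participants makes no exception for withdrawn women, and adverse events are to be recorded throughout. "Withdrawn" may be loose wording for stopping treatment. The triggering event is itself recorded, with its severity and relation to treatment. Acupuncture ends by week 12, and weeks 24 and 36 appear as outcome time points only in Table 1, so a late withdrawal may cost no named efficacy outcome. What removes her from the analysis is the complete-case rule, which affects every dropout. The effect is small under any reasonable assumption.

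Much of this stands. The effect is small, the trigger is narrow, and the wider clash between complete cases and intention to treat is a separate problem. The two mitigating sentences help in part, but a general effort to recover missing data does not keep a withdrawn woman on the schedule, and logging events does not collect VAS-BP, NDBP or quality of life. Nor would a better missing-data method remove the point: it would still leave these women unobserved, when the protocol could simply go on observing them. If continued follow-up was intended, one sentence settles it.

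**Conclusion.** The concern holds. As worded, the rule ends study participation where stopping acupuncture would do, and with complete-case analysis it sits badly with the stated intention-to-treat principle.

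No large bias is claimed. The direction is uncertain, and the tabulated sizes rest on assumed responses, because the plan gives neither an event rate nor outcomes after an event. The loss of scheduled safety data needs no assumption about bias, only the literal reading of the rule. This is a change that should be made because it is cheap and protects data that can be obtained. Confidence is medium, since the sponsor may have meant only that treatment stops.

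**What to change.** Replace the last sentence of section 4 with: *If an adverse event is severe and related to the trial, study acupuncture is stopped and medical care is provided. Unless she withdraws consent, the woman continues the VAS-BP and NDBP diary, the questionnaires and the safety assessments at their scheduled times to week 36, and has the week-12 ultrasound where clinically acceptable.* Acceptability and blinding are tied to the last treatment at week 12, so say whether they are asked when acupuncture stops.

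Add to the SAP: *Data collected after acupuncture is stopped are analysed in the randomised arm.* It would help to say there whether complete case applies per visit or per patient. Other dropouts need a missing-data method of their own.

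The cost is a sentence or two in each document and some follow-up effort for what is likely to be at most a few women. The assessments are already scheduled.

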#### 5. Results Point of Contact

[name], Chief physician, Department of Acupuncture and Moxibustion, Beijing Pinggu District Hospital of Traditional Chinese Medicine, 101200, Beijing, China.[name], [[contact]](mailto:[contact])

Figure 1. Flow chart of participants through the proposed trial.

The schedule of the whole procedure is shown in Table1

Table1 Study period.

	STUDY PERIOD						
	Enrolment	Allocation	Treatment			Follow up	
Timepoint(W,week)	-2	0	4	8	12	24	36
ENROLMENT							
Eligibility screen	X						
Informed consent	X						
Allocation		X					
Interventions							
Manual acupuncture			◆—————◆				
Sham acupuncture			◆—————◆				
Assessment							
VAS-BP	X	X	X	X	X	X	X
NDBP	X	X	X	X	X	X	X
WHOQOL-BREF		X			X		
Breast glandular thickness		X			X		
Breast duct width		X			X		
Patients' global improvement assessment					X		
Patients'acceptability			X		X		
Blindness assessment					X		
Safety assessment			X	X	X	X	X

